Hypothesis: Treatment with glargine U300 will result in equivalent glycemic control in hospitalized patients with T2D. Glargine U300 will result in lower number of hypoglycemia compared to glargine.

Aim 2: To determine differences in glycemic control after hospital discharge between treatment with glargine U300 and glargine U100 in medicine and surgery patients T2D. Patients with poorly controlled diabetes ($HbA1c \geq 7.5\%$) enrolled in Aim 1 will be invited to participate in this open label prospective outpatient study. The total duration of the study is 3 months. Patients with an $HbA1c$ between 7.5% and 10% will be discharged on preadmission oral antidiabetic agents plus glargine U300 and U100 once daily. Patients with an admission $A1C \geq 10\%$ will be discharged on basal bolus regimen with glargine and glulisine insulin before meals.

Hypothesis: treatment with glargine U300 and U100 will result in a similar improvement in HbA1c levels after hospital discharge. Glargine U300 will result in lower number of hypoglycemia compared to U100.

II. BACKGROUND AND CURRENT STATUS OF WORK IN THE FIELD.

Inpatient glycemic control in non-ICU setting. A large body of evidence has shown that in hospitalized patients, the presence of hyperglycemia and diabetes is associated with increased risk of complications and death (1-6, 28-31). Several randomized multi-center trials have shown that the use of basal bolus insulin regimen result in improved glycemic control and reduced rate of hospital complications compared to sliding scale regular insulin (SSI) in patients with T2D (12-14). We have reported that treatment with basal and basal bolus regimens using glargine U100 results in greater improvement in BG control and a reduction in the frequency of hospital complications including postoperative wound infection, pneumonia, bacteremia, and acute renal and respiratory failure compared to SSI treatment.(16, 17, 32, 33) In addition, the use of basal bolus regimen with glargine U100 is safe with low rate of hypoglycemic events. Based on these studies and others, clinical practice guidelines for the management of hyperglycemia in non-ICU setting have favored the use of basal prandial insulin regimens with insulin analogs for most inpatients with T2D (6, 19, 31).

Efficacy and safety of new glargine U-300 insulin:

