The primary outcome of the study is to determine differences in glycemic control as measured by mean daily blood glucose concentration between treatment groups. For each subject, we will take the average of all pre-meal and bedtime glucose values collected after the first day of therapy during the hospital stay (up to 10 days).

Secondary outcomes include differences between treatment groups in any of the following measures:

1. Differences in mean daily glucose in patients admitted to medicine and surgery services.
2. Differences in mean daily glucose in patients with admission HbA1c lower than and higher than 8%.
3. Differences in mean daily glucose in patients with length of stay shorter and longer than 3 and 5 days.
4. Proportion of BG readings within target of 80 mg/dl and 180 mg/dl before meals.
5. Number of BG readings between 80 mg/dl and 180 mg/dl before meals without hypoglycemia.
6. Number of patients with hypoglycemia (defined as a BG < 70 mg/dl) and number of events adjusted by length of stay (event rate).
7. Number of patients with severe hypoglycemia (defined as a BG < 40 mg/dl) and number of events adjusted by length of stay (event rate).
8. Length of hospital stay.
9. Cardiac complications are defined as myocardial infarction, cardiac arrhythmia requiring medical treatment, or cardiac arrest.
10. Acute renal failure defined as a clinical diagnosis with documented new-onset abnormal renal function (increment in serum creatinine > 0.5 mg/dL from baseline).
11. Hospital mortality.

IV.d. Plan. This study will include male or female subjects > 18 years. Due to the design of this study, there will be no run-in period. Upon arrival to the emergency department or medical or general surgical wards, subjects will be screened. Patients with a known history of T2D treated with diet alone, any combination of OADs, and insulin prior to admission will be considered potential candidates for this study. Patients treated with degludec, glargine U300 or with long-acting GLP1-RA (dulaglutide, albiglutide and weekly exenatide) prior to admission will be excluded. Patients admitted with acute or chronic medical illnesses, emergency or elective surgical procedures and trauma would be included in the study. The goal of insulin therapy is to maintain fasting and pre-meal blood glucose levels between 80 mg/dl and 180 mg/dL while avoiding hypoglycemia.

A total of 180 patients with T2D with a blood glucose > 140 mg/dL and < 400 mg/dL will be randomized to receive:

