events, number of severe hyperglycemia, mean daily fasting BG, daily insulin dose, length of hospital stay, acute renal failure and hospital mortality. Blood glucose will be measured before each meal and at bedtime. For discrete outcomes (such as hypoglycemia outcomes), if the outcome is binary (e.g. with or without hypoglycemia), we will first conduct nonparametric comparisons based on a two-sided Chi-square test (or Fisher's exact test in the presence of low incidence rates), followed by the Cochran-Mantel-Haenszel test, which adjusts for the potential center effect. If the discrete outcome is a count outcome (such as the number of hypoglycemic event), we will perform Poisson regression (or Negative Binomial regression) that adjusts for the length of hospital stay to assess the difference in the count outcome between the treatment groups. We also value the repeated measures analyses based on mixed effect models. This is because they will allow us to assess treatment effect fine tuned according to other confounders of the BG outcomes. By these considerations, we will conduct both types of analyses to provide a thorough evaluation of the hypothesis of interest. For continuous outcomes that are not repeated measures (such as length of hospital stay), we will use two-sample t-tests or nonparametric Wilcoxon tests to compare them between groups. Transformations will be applied if normality violation is detected. Multivariate linear regression will be further conducted to assess the difference in continuous secondary outcomes between the two groups while other relevant covariates. We will use standard model selection and model checking procedures for linear regression to decide the final models and assess their fits to the data.

IV.f. Data and Safety Monitoring Board (DSMB):

The Data and Safety Monitoring Board (DSMB) will review unblended data on safety, treatment compliance, and evaluate the efficacy of the intervention being studied in this clinical trial. The DSMB will meet at 6-month intervals and report on study progress to the IRB.

IV.g. Interim Analysis and Stopping Rules: We plan to perform one interim analysis on the primary endpoint every 6 months and when half of the subjects have been randomized. The trial will be stopped if there is evidence beyond a reasonable doubt of a difference in the rate of death and hospital complications (two-sided alpha level, <0.01) between the treatment groups.

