If any FBG or RBG 40- 69 mg/dl	Decrease by 8 IU or 20% of total daily dose
If any FBG or RBG < 40 mg/dl	Decrease total daily dose by 30 - 40%

V.g. Aim 2. Statistical Analysis:

V.g.1. Sample Size and Power Calculations: The primary endpoint in Aim 2 is difference in glycemic control (mean daily BG) after hospital discharge. Under the same assumptions for equivalence margin and BG variability as in Aim 1, we have the same sample size requirement (i.e. 78 subjects per group after 10% attrition). Accounting for 10% attrition rate, we would need 90 patients per treatment group (total # of patients to be recruited: 180 subjects, 90 per treatment group), to achieve >80% power.

V.g.2. Analysis of Primary Endpoint:

The primary endpoint in this study is glycemic control measured by mean daily BG concentration after hospital discharge. Secondary outcomes include rate of hypoglycemia during follow-up, change in HbA1c, body weight in kilograms, number of episodes of severe hyperglycemia, complications and emergency room visits or hospital readmissions at 12 weeks post-discharge. To analyze these outcomes, we will follow the same analytic strategy proposed for the secondary endpoints of Aim 1. We will first compare the primary outcome using two-sample t-tests (or Wilcoxon tests) or one-way ANOVA, followed by multivariate linear regression to estimate and test the difference between the two treatment groups while simultaneously accounting for other potential confounders. Transformations will be applied if normality violation is detected. Stepwise, backward, or forward model selection strategy will be adopted to determine the variables to be included in the final model. Standard diagnostic and model checking procedures will be applied to examine the fit of the developed models.

DATA HANDLING AND RECORD KEEPING:

Data collection records with personal identifiers will be stored in locked file cabinets. Presentation of the study results at regional or scientific meetings or in publications will not identify subjects. Access to research and confidential records will be limited to clinical investigators, research coordinators, and the IRB at Emory University.

All data will be entered electronically in Redcap by participating sites. Sponsor site expects data to be entered in Redcap within 10 days of phone call or outpatient visit.

VI. Methods and Procedures Applied to Human Subjects:

VI.a. Subject Population:

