per kg of body weight) in patients ≥ 70 years of age and/or eGFR < 60 ml/min. To avoid hypoglycemia, the total daily dose of insulin will be decreased by 10% for BG between 70-99 mg/dl and by 20% after each episode of hypoglycemia (BG < 70 mg/dl). In addition, in patients treated with insulin at home, the TDD of insulin will be reduced by 20% on admission and the attending physician may further reduce insulin dose in the presence of severe hypoglycemia.

Hypoglycemia will be treated with dextrose infusion. Dextrose 50% solution will be given for glucose values < 70 mg/dl. If the patient is awake, 25 ml (1/2 amp) will be given IV or oral juice/snack (crackers) as per protocol. If the patient is not awake: 50ml (1 amp) will be given STAT. Blood glucose levels will be repeated in 15 minutes and dextrose administration will be repeated as needed for values < 70 mg/dl.

XI. Inclusion of women.

We anticipate that ~50% of the study subjects will be female. Absence of pregnancy must be demonstrated by blood or urine testing prior to randomization (in female subjects of child bearing potential only). Glargine U300 and U100 have not been approved during pregnancy.

XII. Inclusion of minorities.

Patients will not be excluded based on race or ethnic origin. We anticipate that approximately one-third of patients will be African Americans, Hispanics, and Caucasians.

XIII. Inclusion of children.

No patients under the age of 18 will be recruited in this study.

XIV. Payment for participation.

Participation in this study is voluntary. Patients will receive one hundred dollars (\$100.00) during the hospital stay. If a participant should stop participation before completion, the payment will be prorated at \$10.00 per day. Participants will receive seventy- five dollars (\$75.00) after each clinic visit at 1 and 3 months after discharge. Total compensation will be two hundred and fifty dollars (\$250.00).

XV. Financial conflict of interests.

This study receives support from Sanofi. [name] serves as a consultant to Sanofi and receives compensation for these services. The terms of this arrangement have been reviewed and approved by Emory University in accordance with its conflict of interest policies.

XVI. Pharmacovigilance specifications

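### The hypoglycemia superiority hypotheses have no lead analysis, no rule for Poisson versus negative binomial, and no stated time at risk after discharge; false positives rise if Poisson is kept while events cluster within patients

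*Combined protocol and SAP*

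**What the plan says.** The Aim 1 hypothesis under Specific Aims reads "Glargine U300 will result in lower number of hypoglycemia compared to glargine", and the Aim 2 hypothesis repeats the claim against U100. Section IV.c lists the endpoint among the secondary outcomes in two forms: "Number of patients with hypoglycemia (defined as a BG < 70 mg/dl) and number of events adjusted by length of stay (event rate"). Its next item does the same for BG <40 mg/dl.

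The secondary-endpoint section of IV.g Data Analysis sets out these steps:

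- Binary outcome: a comparison "based on a two-sided Chi-square test" (Fisher's exact test if incidence is low), "followed by the Cochran-Mantel-Haenszel test, which adjusts for the potential center effect".
- Count outcome: "we will perform Poisson regression (or Negative Binomial regression) that adjusts for the length of hospital stay".
- Mixed-effect models are also valued, and "we will conduct both types of analyses to provide a thorough evaluation of the hypothesis of interest".

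The section gives no alpha for hypoglycemia, no order among the analyses and no dispersion check. Its model-checking sentence concerns linear regression. The prior-insulin stratum used for randomization (IV.e) does not appear in the analysis.

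For Aim 2, section V.g.2 states that "we will follow the same analytic strategy proposed for the secondary endpoints of Aim 1". Section X.a expects about 10% of patients to have hypoglycemia in hospital and about 20% after discharge. It also reduces the insulin dose "by 20% after each episode of hypoglycemia (BG < 70 mg/dl"), so more than one episode in a patient is foreseen.

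**The concern.** Poisson regression takes the variance of the count to equal its mean, given the covariates. If some patients are more prone to hypoglycemia than others, the variance is larger, the Poisson standard error is too small and the test rejects too often. Negative binomial regression handles this, and the plan permits it. But nothing says when it applies, and the trial is open label, so the choice could be made with event counts by arm in view.

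Two further gaps bear on the same hypothesis. First, with several analyses and none named as deciding, a reader of the results cannot tell which one the claim rests on. Second, the only exposure adjustment named is length of hospital stay. That is not the time at risk for Aim 2, where events accrue over 12 weeks after discharge.

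At stake is whether a statement that U300 causes less hypoglycemia can be taken at its nominal error rate.

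**Working it through.** **The plan's own figure.** The only design calculation is for mean daily glucose: margin 18 mg/dl, SD 45 mg/dl, true difference 0, one-sided test, 80% power. Alpha is not stated; 0.05 reproduces the result: n = 2 × (45/18)² × (1.645 + 0.842)² = 12.5 × 6.185 = 77.3, so 78 per group. There is no corresponding calculation for hypoglycemia, and hence no stated error rate or dispersion to reproduce.

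**Inputs.** From X.a: proportion affected p = 0.10 inpatient and 0.20 outpatient. Assumed, because the documents do not give it: mean events per affected patient e, taken as 1.25-2.0 inpatient and 1.5-3.0 outpatient. Also assumed: nominal two-sided 0.05 and gamma-distributed patient rates.

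**Closed-form check.** The mean count is m = p × e. With gamma shape k, P(no event) = (1 + m/k)^(−k) = 1 − p, which fixes k. The variance-to-mean ratio is D = 1 + m/k. The Poisson standard error is too small by a factor √D, so a nominal 5% test has actual two-sided error 2 × [1 − Φ(1.96/√D)]. Equal follow-up is taken within each setting.

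| Setting | e | m | k | D | 1.96/√D | Actual two-sided error |
|---|---|---|---|---|---|---|
| Inpatient | 1.25 | 0.125 | 0.317 | 1.39 | 1.66 | 9.7% |
| Inpatient | 1.5 | 0.15 | 0.157 | 1.95 | 1.40 | 16% |
| Inpatient | 2.0 | 0.20 | 0.090 | 3.22 | 1.09 | 27% |
| Outpatient | 1.5 | 0.30 | 0.395 | 1.76 | 1.48 | 14% |
| Outpatient | 2.5 | 0.50 | 0.155 | 4.23 | 0.95 | 34% |
| Outpatient | 3.0 | 0.60 | 0.1287 | 5.66 | 0.82 | 41% |

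**Simulation with no treatment effect.** 4,000 trials per scenario, 90 per arm, inpatient stay varying from 2 to 10 days, outpatient follow-up 12 × 7 = 84 days, log exposure as offset:

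- Inpatient Poisson (likelihood ratio test): 9.6%, 16.6% and 28.9% at e = 1.25, 1.5 and 2.0. Negative binomial: 5.9%, 5.6% and 6.4%.
- Outpatient Poisson: 12.9% at e = 1.5 and 34.7% at e = 2.5. Negative binomial: 4.7% and 5.4%.
- With 81 per arm (90 less 10% attrition), Poisson gave about 7-27% inpatient and 12-41% outpatient, the upper outpatient end at e = 3.0. Robust variance gave about 4-8%. In the 90-per-arm runs robust variance reached 9.2% in the worst inpatient case, which is why negative binomial is the better first choice.

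**Direction.** With 1:1 allocation and no effect, about half of the false results favour U300. Inpatient Poisson in that direction: 4.5%, 8.2% and 14.5% against a nominal 2.5%.

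**Overlapping tests.** With no over-dispersion, at least one of chi-square, Cochran-Mantel-Haenszel and Poisson was significant in 6.3% of null trials, because the tests are highly correlated. With negative binomial as the count model, the any-test figure was 5.9-8.6% across the inpatient scenarios.

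**The case against.** The strongest reply is that the plan already names the remedy. A reader might infer that it commits to plain Poisson, but the quoted sentence offers negative binomial in the same breath. Switching to negative binomial when a dispersion test is significant holds the inpatient count test at 4.8-6.9%, so an analyst who checks would be safe. This stands, and it removes any claim that the plan as written must inflate error. What it leaves is that neither the check nor the rule is written down.

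A reader might also infer that a false claim of less hypoglycemia is far likelier than 5%. The documents do not support that. It requires Poisson to be kept despite clustering, only about half the rejections point towards U300, and the events-per-patient figure is assumed. The dose-reduction instruction in X.a shows that repeat episodes are foreseen, not that they are frequent, and repeat episodes alone are compatible with Poisson.

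Nor does the number of tests do much harm within one aim: it adds about one percentage point without over-dispersion. The BG <40 mg/dl analyses are a separate listed outcome, and the plan nowhere says that any one significant test is enough.

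On Aim 2, adopting the same strategy need not mean using hospital days as outpatient exposure, and a sensible analyst would use days after discharge. That reading is fair, but the text does not state it. A specific bias from unequal follow-up cannot be claimed, since it would rest on differential drop-out that the plan does not describe.

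Finally, hypoglycemia is secondary and the plan promises no confirmatory error control for it. Against that, both aims state a directional hypothesis on it, so one identified lead analysis is a modest request.

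**Conclusion.** The point holds in a conditional form. Three things are missing from the text: a lead hypoglycemia analysis for each aim, a rule for Poisson versus negative binomial, and the exposure time for post-discharge events.

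If Poisson is kept and events cluster, two-sided type I error is about 7-29% inpatient and 12-41% outpatient, with roughly half of that favouring U300. Negative binomial or robust variance brings it to about 4-8%, apart from the one worst-case robust result noted above. If events do not cluster, there is little to correct. The sizes depend on the assumed 1.25-2.0 (inpatient) and 1.5-3.0 (outpatient) events per affected patient and on gamma-distributed rates. The incidences are the plan's own. Mixed models with selected covariates and the six-monthly looks at hypoglycemia were not simulated.

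This should be settled before the data are analysed, but it does not threaten the primary comparison.

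**What to change.** For each aim, name one lead hypoglycemia analysis in the SAP:

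- Outcome: rate of BG <70 mg/dl events.
- Model: negative binomial regression; Poisson with robust variance if it does not converge.
- Exposure: an offset of log days observed in that aim, meaning inpatient days for Aim 1 and days after discharge for Aim 2. For Aim 1, days observed can differ from length of stay, because the inpatient flow chart ends at day 10.
- Covariate: the prior-insulin randomization stratum.
- Level: two-sided 0.05, stated.

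Report the remaining hypoglycemia analyses (proportion affected, Cochran-Mantel-Haenszel, mixed models, BG <40 mg/dl) as supportive, with confidence intervals. Testing hypoglycemia only after the 18 mg/dl comparison succeeds is an option, not a requirement.

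The cost is SAP wording, with no change to enrolment or patient care. The only data needed are the days each patient was observed in each aim. When events cluster, intervals will be wider than Poisson's, and the other tests can no longer carry the claim.
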